14.5 Previous and concomitant medication

Previous and concomitant medication (ticked as type=concomitant medication in the eCRF) will be coded according to WHO-Drug Dictionary DDE 2017-01 or higher.

All prior and concomitant medications will be listed as documented in the CRF. In this listing the WHO-Drug coding including the drug name as documented in the CRF, the drug name used for the coding, the Preferred Term, the ATC-Code and the ATC-Term will be included as well. Coding will be done using ATC level 4, which will be presented in listings. Summary tables of the WHO-Drug coding will be prepared by ATC Class (ATC Level 2 shown) and Preferred Term presenting number/ percentages of medication applied. All other details concerning medication will be listed and not tabulated.

The distinction between previous and concomitant medication will be done as follows (in case of missing date parts use sec. 9).

- Prior medication is all medication which stopped before first IMP administration within the trial context independent from start date.
- Concomitant medication is all medication that started prior first IMP administration and are still ongoing/ stopped at date of first study drug intake, or medication that started at/ after date of first drug intake.

15. PHARMACOKINETIC (PK) AND PHARAMCODYNAMIC (PD) PROPERTIES

Pharmacokinetic and pharmacodynamic endpoints

Pharmacokinetic and pharmacodynamic characteristics are assessed by using the following endpoints:

1. Pharmacokinetics: Plasma dasiglucagon and GlucaGen® (glucagon) concentrations from 0-90 min after dosing will be evaluated based on the following endpoints: $AUC_{0-30\text{min}}$, $AUC_{0-90\text{ min}}$, C_{max} , t_{max} . Samples will be taken at visit 2 and visit 4 after first and third administration of trial medication. Samples will be collected pre-dose, and at 5, 10, 30, 60, and 90 min post-dosing.
2. Pharmacodynamics on plasma glucose concentrations after administration of first and third doses of trial medication. Samples will be collected pre-dose, and at 5, 10, 30, 60, and 90 min post-dosing:
 - Plasma glucose profiles over the period from 0-90 min after dosing will be evaluated based on the following endpoints: $AUE_{0-30\text{min}}$, $AUE_{0-90\text{ min}}$, CE_{max} , t_{max}
 - Achieving a plasma glucose increase of ≥ 20 mg/dL within 30 minutes after treatment

16. METHODS OF PHARMACOKINETIC (PK) AND PHARAMCODYNAMIC (PD) ENDPOINT ANALYSIS

Pharmacokinetic and pharmacodynamic analyses will use the PKs population.

16.1 PK and PD parameters

The pharmacokinetic metrics as listed below will be obtained from individual plasma concentration-time data by non-compartmental analysis using the computer programs WinNonLin® Version 5.4 or SAS Version 9.4.

The following PK parameters will be calculated for dasiglucagon and GlucaGen® analytes from the individual plasma concentration versus time profiles after each active treatment per visit.

Symbol	Definition	Calculation
C_{\max}	Measured maximum serum concentration after administration	Taken directly from analytical data, selected from individual concentration data
t_{\max}	Sampling time until reaching C_{\max}	Taken directly from analytical data, selected from individual concentration data
$AUC_{0-30\text{min}}$	Area under the concentration-time curve from zero up to the concentration at 30min	Linear trapezoidal rule for the ascending part of the concentration-time curve, logarithmic trapezoidal rule for the descending part.
$AUC_{0-90\text{min}}$	Area under the concentration-time curve from zero up to the concentration at 90min	Linear trapezoidal rule for the ascending part of the concentration-time curve, logarithmic trapezoidal rule for the descending part.

Table 2: Pharmacokinetic metrics

The following PD measures for glucose will be calculated from the plasma results for each treatment group and visit:

Symbol	Definition	Calculation
CE_{\max}	Change from baseline plasma glucose to maximum plasma glucose measured post-dose	Taken directly from analytical data, selected from individual concentration data
t_{\max}	Time to maximum change from baseline CE_{\max}	Taken directly from analytical data, selected from individual concentration data
$AUE_{0-30\text{min}}$	Area under the baseline-adjusted effect curve from zero up to the concentration measured at 30min	Linear trapezoidal rule for the ascending part of the effect-time curve, logarithmic trapezoidal rule for the descending part.
$AUE_{0-90\text{min}}$	Area under the baseline-adjusted effect curve from zero up to the concentration measured at 90min	Linear trapezoidal rule for the ascending part of the effect-time curve, logarithmic trapezoidal rule for the descending part.

Symbol	Definition	Calculation
Inc20 _{0-30min}	Increase of ≥ 20 mg/dL within 30 minutes after treatment	Binary variable derived from raw glucose concentration measured at 30min after dosing. In case glucose has reached at least 20 mg/dL the parameter is set to 'yes', otherwise to 'no'

Table 3: Pharmacodynamic metrics

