Incidence calculated as percentage of baseline ADA-positive patients with significant increases (≥ 5 -fold) in ADA titer after drug administration and the total number of evaluable patients, excluding baseline-positive patients without any samples available after drug administration.

Secondary endpoints:

Characterization of ADA response:

- Incidence and titer of neutralizing activity of ADA positive patients
- Incidence of cross-reactivity of ADA positive patients towards endogenous glucagon
- Kinetics of ADA:
The timing and duration of detected ADA response

Safety:

- The incidence, type and severity of AEs
- Changes from baseline in clinical laboratory parameters
- Changes from baseline in vital signs
- Clinically meaningful changes from baseline in physical examination and electrocardiogram (ECG)

Exposure endpoints, after administration of first and third doses of trial medication:

- Plasma dasiglucagon and glucagon concentrations from 0-90 min after dosing will be evaluated based on the following endpoints: $AUC_{0-30\text{min}}$, $AUC_{0-90\text{min}}$, C_{max} , t_{max}

Pharmacodynamics after administration of first and third doses of trial medication:

- Plasma glucose profiles over the period from 0-90 min after dosing will be evaluated based on the following endpoints: $AUE_{0-30\text{min}}$, $AUE_{0-90\text{min}}$, CE_{max} , t_{max}
- Achieving a plasma glucose increase of ≥ 20 mg/dL within 30 minutes after treatment

7. Investigational plan

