7.4.2 Treatments administered

Dasiglucagon is a stable peptide analog of human glucagon in a ready-to-use liquid formulation indicated for treatment of severe hypoglycemia in insulin dependent patients with diabetes mellitus. Dasiglucagon is in clinical development and has no marketing authorization as yet. GlucaGen is approved in the EU and US and is indicated for treatment of severe hypoglycemic reactions, which may occur in the management of insulin-treated children and adults with diabetes mellitus.

Patients in this trial have not previously been treated with dasiglucagon (ZP4207) and will be randomly assigned (1:1) to receive 1 of the following trial medications:

- 0.6 mg dasiglucagon
- 1 mg GlucaGen

Prior to administration of trial medication at all dosing visits patients must reach a target plasma glucose level of 70-150 mg/dL. If the patient presents with plasma glucose > 150 mg/dL, corrective amounts of fast acting insulin will be administered at the investigator's discretion. Plasma glucose measured after 20 and after 40 minutes should ensure that the patient has reached the targeted 70-150 mg/dL. If the patient presents with plasma glucose < 70 mg/dL glucose ingestion will be provided in order to reach target plasma glucose of 70-150 mg/dL documented by plasma glucose measurements after 20 and 40 minutes, respectively.

Following the first (Visit 2) and third (Visit 4) dose administration, patients must be fasting for 90 min after dosing. Following the 90-min blood sample draw after the administration of the first (Visit 2) and third (Visit 4) dose administration, patients may be treated individually in order to alleviate any potential side effects in order to minimize premature treatment discontinuation and consequently reduce the amount of missing data. This treatment can also be instituted immediately after the second dose administration (Visit 3), as pharmacodynamics will not be assessed at this visit.

In order to minimize the number of patients discontinuing treatment prematurely and consequently reduce the amount of missing data, the following treatment modalities may be used, as considered appropriate by the investigator:

At visit 2 and 4:

- 90 min after dosing patients will be allowed to eat and drink moderately to make them feel comfortable
- 90 min after dosing a moderate and individualized corrective dose of insulin to convert the induced hyperglycemia to euglycemia, after agreement with the investigator

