7.6.1 Immunogenicity measurements

Antibodies against dasiglucagon/glucagon will be measured at all visits after screening. During the treatment period (Visits 2, 3, and 4) samples will be collected pre-dose as well as at unscheduled dosing visits for ADA positive patients.

The ADA samples will be analyzed at a special laboratory (refer to Appendix 1). Samples collected at the planned visits will be analyzed in batches at three occasions during the trial and any positive results will immediately be communicated to the investigator in a blinded manner.

The clinical ADA assays have been validated in accordance with existing guidelines and recommendations.^{6,7,8,9,10}

Confirmed positive anti- dasiglucagon antibody samples, (treatment-induced or treatment-boosted) from anti-dasiglucagon antibody-positive patients will be evaluated for binding titer neutralizing potential and titer as well as cross-reactivity towards endogenous glucagon.

No further serum sampling will be needed as the ADA samples can be used for Nab analysis.

The *in vitro* neutralizing effect of antibodies will be measured using an assay^{9,12} based on glucagon receptor transfected human embryonic kidney cells. The calculated sensitivity in previous studies was about 51.8 ng/mL. The assay was also validated for recombinant glucagon with similar results.^{11,12} In case of a positive result in the Nab assay, a titer estimation will be performed. The cell-based Nab analyses will be performed by a special laboratory, BioAgilytix, Durham, NC, USA.

In vivo neutralizing effect will be evaluated by comparing PK and PD endpoints between ADA positive and ADA negative patients, further investigation may be performed by correlating ADA titer with PK and PD endpoints.

Residual and additional antibody serum samples may be stored until approval of market authorization by the health authorities. Further characterization of the antibody response may be requested by the health authorities.

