8.4 Hypoglycemia

Hypoglycemia will be regarded as an AE and recorded and documented on an AE Form.

Hypoglycemia is defined as a fall of plasma glucose below 3.9 mmol/L (70 mg/dL).

During the dosing visits, mild to moderate symptoms of hypoglycemia, or a blood glucose (BG) value less than a threshold of <2.8 mmol/L (50 mg/dL), corresponding to a plasma glucose (PG) value of <3.1 mmol/L (56 mg/dL), will be treated by i.v. glucose solution at the investigator's discretion according to best available medical practice. Treatment is to be repeated until BG value stabilized above the threshold limit again. BG measurements will only be done due to safety concerns. Insulin-induced hypoglycemia should be recorded as an AE.

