16.2 Data handling

Serial blood samples for pharmacokinetic and pharmacodynamic assessments will be drawn at the following intervals: pre-dose and 5min \pm 1min, 10min \pm 1min, 30min \pm 1min, 60min \pm 1min and 90min \pm 1min after start of dosing.

Summary tables for raw plasma concentrations, evaluation of concentration versus time data:

- i.) *For all pre-dose samples, the sampling time will be set to zero.*
- ii.) *For post-dose samples, the planned sampling time will be used in summary tables and the actual sampling times will be used for all figures of individual concentrations*
- iii.) *All pre-dose concentration values $< LLOQ^{[1]}$ will be set to zero.*
- iv.) *Post-dose concentration values $< LLOQ$ after t_{max} will be set to zero if there are no further concentrations $> LLOQ$ at later time points.*
- v.) *Post-dose concentration values $< LLOQ$ after t_{max} will be set to the lower limit of quantitation if there are further concentrations $> LLOQ$ at later time points.*
- vi.) *Missing post-dose values will not be replaced.*

Determination of PK/PD metrics:

- i.) *For all pre-dose samples, the sampling time will be set to zero.*
- ii.) *For post-dose samples, the actual sampling time will be used.*
- iii.) *All pre-dose concentration values will be set to zero.*
- iv.) *Post-dose concentration values $< LLOQ$ before t_{max} will be set to zero if there are no further concentrations $> LLOQ$ at later time points.*

^[1] LLOQ: Lower Limit of Quantification

- v.) *Post-dose concentration values < LLOQ before tmax will be set to the lower limit of quantitation if there are further concentrations > LLOQ at later time points.*
- vi.) *Post-dose concentration values < LLOQ after tmax will be ignored if there are no further concentrations > LLOQ at later time points.*
- vii.) *Post-dose concentration values < LLOQ after tmax will be set to the lower limit of quantitation if there are further concentrations > LLOQ at later time points.*
- viii.) *Missing post-dose values will not be replaced.*

PK and PD metrics will be determined by SynteractHCR. Plasma concentration data will be transferred from external laboratory (York Bioanalytical Solutions (YBS), MLM laboratories) to SynteractHCR as detailed in separate data transfer specifications.

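### The glucose-response endpoints credit the drug with any rise that follows rescue glucose in the 0-90 min window, and no analysis rule covers such values

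*SAP*

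**What the plan says.** SAP 16.1 (Table 3) derives the pharmacodynamic metrics from plasma glucose sampled pre-dose and at 5, 10, 30, 60 and 90 min. CEmax is "Change from baseline plasma glucose to maximum plasma glucose measured post-dose"; AUE0-90 is "Area under the baseline-adjusted effect curve from zero up to the concentration measured at 90min". Protocol section 6 adds a binary endpoint, "Achieving a plasma glucose increase of ≥ 20 mg/dL within 30 minutes after treatment". The SAP derives it from the raw 30 min value: "In case glucose has reached at least 20 mg/dL the parameter is set to 'yes', otherwise to 'no".

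Glucose can reach the patient by two routes around this window:
- **After dosing.** Under Protocol 8.4, a patient with mild to moderate hypoglycemic symptoms, or with blood glucose under 50 mg/dL (plasma glucose under 56), "will be treated by i.v. glucose solution at the investigator's discretion according to best available medical practice". Treatment is repeated until the value is stable.
- **Before dosing.** Under Protocol 7.4.2, if plasma glucose is below 70 mg/dL, "glucose ingestion will be provided in order to reach target plasma glucose of 70-150 mg/dL", with checks at 20 and 40 min.

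On data handling, SAP 16.2 says "Missing post-dose values will not be replaced" and otherwise covers sampling times, pre-dose values and values below the quantification limit. Protocol 7.6.1 states one use of these endpoints: "In vivo neutralizing effect will be evaluated by comparing PK and PD endpoints between ADA positive and ADA negative patients".

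**The concern.** The endpoints are meant to measure glucose mobilized by the drug. Once glucose has been infused, later samples no longer measure that, yet the derivations use them as if they did. The 90 min fast at Visits 2 and 4 shows that the window was meant to be protected, but it restricts food, not i.v. rescue.

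The direction of the error matters. A patient whose drug works has little need of rescue; one whose drug is neutralized, perhaps after corrective insulin before dosing, is more likely to need it. The rise after rescue is then recorded as response in the kind of patient that the antibody comparison is designed to find.

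**Working it through.** **1. Planning figures.** The plan gives no figure for the glucose endpoints. The figures used below come from the ADA sample size (SAP section 5): ln(0.10)/ln(0.95) = 44.9, so 45 completers per arm; the chance of at least one event at a 5% rate is 1 - 0.95^45 = 0.9006. The plan's 45 is reproduced.

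**2. Search for a rule.** SAP section 9 uses observed values only. The PK/PD set in SAP section 8 does not exclude rescued patients. SAP 16.1 and 16.2 do not mention administered glucose, and neither does the deviation list in section 3.3 of the data review meeting document. No rule was found.

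**3. Effect on one patient.** The changes from baseline are assumed. Times are 5, 10, 30, 60 and 90 min. The linear rule is used throughout, because a logarithmic rule cannot be applied to negative changes.
- A, drug failure without rescue: -3, -8, -12, -12, -10 mg/dL.
- B, the same patient with i.v. glucose between 10 and 30 min: -3, -8, +40, +20, 0.
- C, patient B with the last pre-rescue change (-8) carried forward from 10 min.

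AUE0-30, in mg·min/dL:
- A: -7.5 - 27.5 - 200 = -235
- B: -7.5 - 27.5 + 320 = +285
- C: -7.5 - 27.5 - 160 = -195

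AUE0-90:
- A: -235 - 360 - 330 = -925
- B: 285 + 900 + 300 = +1485
- C: -195 - 240 - 240 = -675

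| Case | CEmax | tmax (min) | AUE0-30 | AUE0-90 | Rise of 20 by 30 min |
|---|---|---|---|---|---|
| A | -3 | 5 | -235 | -925 | no |
| B, all values (as planned) | +40 | 30 | +285 | +1485 | yes |
| C, proposed rule | -3 | 5 | -195 | -675 | no |

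**4. When rescue crosses the threshold.** The rise must at least equal the prior fall plus 20 mg/dL. With value-triggered rescue at a plasma glucose of 56:
- Baseline 70: (70 - 56) + 20 = 34 mg/dL.
- Baseline 150: (150 - 56) + 20 = 114 mg/dL.

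Symptom-triggered rescue has no glucose floor, so the fall can be small and the required rise close to 20.

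The documents give no rescue dose. Assume 5 to 25 g, 70 kg and a glucose space of 0.16-0.25 L/kg. Rise = dose in mg / (70 × space × 10): 5 g gives 29-45, 10 g gives 57-89 and 25 g gives 143-223 mg/dL. Thus 5 g may miss even the 34 needed from a baseline of 70, 10 g meets 34 but not 114, and 25 g meets both.

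**5. Size.** One misclassified patient moves an arm's responder rate by 1/45 = 2.2 points. Expected ADA-positive patients per arm at the planning rate: 45 × 0.05 = 2.25.

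**The case against.** The strongest reply is that the event is rare and the consequence small. Patients are dosed at 70-150 mg/dL; Protocol 5.1 reports that every phase 2 patient rose by at least 20 mg/dL within 30 min; and the endpoints are descriptive. Antibodies induced by the trial drug cannot be present at Visit 2, and Visit 4 (Day 14) precedes the expected peak at Day 35, so the unscheduled dosing visit for ADA-positive patients (Protocol 7.5.6) is the main realistic setting. All of this stands and limits the weight of the point. It does not supply the missing rule.

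Four stronger readings are tempting but not supported:
- **That rescue always turns a failure into a responder.** It does so only when the rise makes good the prior fall plus 20 mg/dL. By 30 min this should be uncommon; CEmax and AUE0-90 are more exposed.
- **That rescue inflates the SAP's binary variable as written.** Taken literally, that variable tests whether raw glucose is at least 20 mg/dL. At a baseline of 70, cases A and B have 30 min values of 58 and 110, and both score yes. That is a separate and larger error; correcting it leaves the rescue gap open.
- **That a reported table will be distorted by about 44 points (1/2.25).** SAP 16.3, 16.4 and Appendix C tabulate the metrics by treatment group and visit. No table by ADA status is planned, and readers would also have individual profiles and listings.
- **That oral glucose before dosing generally creates a false response.** The baseline sample, taken within 5 min of dosing, absorbs the rise already seen. Only absorption continuing after it counts.

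**Conclusion.** The gap is real and modest. Following the stated derivations gives a wrong CEmax, tmax or AUE whenever rescue glucose drives the later samples, and can give a wrong result on the protocol's 20 mg/dL endpoint. The bias is toward hiding loss of effect.

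Across an arm it is about 2 points of responder rate per affected patient. It carries more weight where ADA-positive patients are compared with ADA-negative ones, because about 2 positive patients per arm are expected at the 5% planning rate. The primary ADA endpoint is unaffected.

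The conclusion rests on the absence of any rule in either document. The profiles in the check and the rescue doses are assumptions, and the frequency of rescue is unknown.

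**What to change.** Amend SAP 16.1 and 16.2:

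1. Score the 20 mg/dL endpoint as an increase from the pre-dose value. Count as a non-responder any patient given glucose after dosing and within 30 min who had not yet reached that increase. The rule in 16.2 that sets pre-dose concentrations to zero must not be applied to glucose here.
2. For glucose given after dosing, take CEmax and tmax from samples before it. Flag affected AUEs and compute them with the last pre-rescue change carried forward. Simply deleting later values would make AUE0-90 unavailable for rescued failures and so drop them from the summary. Keep the all-values result as a sensitivity analysis.
3. Repeat the PD metrics table without profiles that had oral glucose in the 40 min before dosing.

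List the carry-forward as an exception in SAP section 9, which otherwise bars imputation. Confirm that the time and route of administered glucose are captured: Protocol 7.4.8 and 8.2 provide for concomitant medication and AE times, but do not show that the clock time of glucose is recorded.

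The cost is SAP wording, one extra sensitivity table (items 2 and 3 can share it) and a few flagged AUE values. No clinical rule for giving glucose changes.

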9. HANDLING OF DROP-OUTS OR MISSING DATA

In general no imputations will be made for missing values. Summaries will be based on observed data/ valid cases only.

There are some exceptions:

1. Any AE with missing relationship will be considered as possibly related to the study drug.
2. For flagging adverse events into pre-treatment/ treatment-emergent and medication into previous and concomitant, the following rules will be applied (the calculation of durations if foreseen won't use imputed data):

Date	Imputation rule
Partial/ Missing Start Date	
 • Missing day - Impute the 1st of the month unless year and month is same as year and month of first dose of study drug or date of screening in case study drug started earlier then impute first dose date • Missing day and month – impute 1st January unless year is the same as first dose date then impute first dose date • Completely missing – impute first dose date unless the end date suggests it could have started prior to this in which case impute the 1st January of the same year as the end date
Partial/ Missing End Date	
 • Missing day - Impute the last day of the month unless year and month is same as year and month of last dose of study drug then impute last dose date • Missing day and month – impute 31st December unless year is the same as last dose date then impute last dose date • Completely missing – impute date of last dose • If imputed end date < imputed start date, take the imputed start date to impute the end date

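### SAP Table 3 applies the logarithmic trapezoid to baseline-adjusted glucose, where it is undefined once the curve falls to or below baseline, and gives no fallback

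*SAP*

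**What the plan says.** Table 3 of SAP 16.1 defines the two glucose areas as "Area under the baseline-adjusted effect curve from zero up to the concentration measured at 30min" and "Area under the baseline-adjusted effect curve from zero up to the concentration measured at 90min". For both, the calculation column reads "Linear trapezoidal rule for the ascending part of the effect-time curve, logarithmic trapezoidal rule for the descending part". Table 2 gives the same rule for drug concentrations.

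The sampling grid is set in SAP 15: "Samples will be collected pre-dose, and at 5, 10, 30, 60, and 90 min post-dosing".

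SAP 16.2 lists the special cases for deriving PK/PD metrics. Before dosing, "All pre-dose concentration values will be set to zero". Post-dose values below the LLOQ are set to zero, set to the LLOQ or dropped, depending on their position relative to tmax; one kind "after tmax will be ignored if there are no further concentrations" above that limit. Missing post-dose values are not replaced. Nothing covers a baseline-adjusted value of zero or less, no linear fallback is stated, and the descending part is not defined. SAP 9 adds: "In general no imputations will be made for missing values". SAP 16.1 allows either of two programs and names no setting for this case.

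The protocol lists both areas as secondary PD endpoints (section 6) and gives no integration rule.

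**The concern.** The logarithmic trapezoid suits drug concentrations, which are positive apart from values below the LLOQ, and those have their own rules. A glucose change from baseline is different: it is zero at time zero by construction and can return to zero or go below it.

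Such values are possible in this trial. Protocol 7.4.2 says: "If the patient presents with plasma glucose > 150 mg/dL, corrective amounts of fast acting insulin will be administered". Protocol 7.5.2 also allows rapid-acting insulin with breakfast on dosing days. Patients then fast for 90 min after dosing at Visits 2 and 4, so insulin may still be acting during sampling.

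If the log segment fails, the patient's AUE is either missing or set by an unstated programming choice. Pharmacodynamic response is part of the secondary objective. Protocol 7.6.1 plans to judge in vivo neutralization by comparing PK and PD endpoints between ADA-positive and ADA-negative patients. Few ADA-positive patients are expected (none among 141 earlier subjects), so one lost or shifted value could matter in that comparison.

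**Working it through.** **Inputs.** The grid is 0, 5, 10, 30, 60 and 90 min (SAP 15) and the rule is that of SAP 16.1, Table 3. The documents give no glucose profiles, so every profile below is an assumption, in mg/dL above baseline. They also state no AUE value, so there is no figure to reproduce.

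**Formulas**, for a segment from E1 to E2 lasting dt:

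- Linear: (E1 + E2) × dt / 2
- Logarithmic: (E1 − E2) × dt / ln(E1/E2), which exists only if E1 > 0 and E2 > 0

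**Late fall.** Take the profile 0, 2, 10, 50, 60, x, with x the value at 90 min.

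- 0–30 min, all rising, so linear: 5 + 30 + 600 = 635. This is AUE0-30min, and it does not depend on x.
- 30–60 min, rising: (50 + 60) × 30 / 2 = 1650, giving 2285 up to 60 min.
- 60–90 min, falling. For x = 10, linear gives (60 + 10) × 30 / 2 = 1050 and log gives 50 × 30 / ln 6 = 837.

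| x at 90 min | Last segment, linear | Last segment, log | AUE0-90, linear | AUE0-90, SAP rule | Difference |
|---|---|---|---|---|---|
| 20 | 1200 | 1092 | 3485 | 3377 | −3.1% |
| 10 | 1050 | 837 | 3335 | 3122 | −6.4% |
| 5 | 975 | 664 | 3260 | 2949 | −9.5% |
| 1 | 915 | 432 | 3200 | 2717 | −15.1% |
| 0 | 900 | undefined | 3185 | undefined | – |
| −5 | 825 | undefined | 3110 | undefined | – |

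Areas are in mg/dL·min.

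**Early return** (0, 2, 10, 50, 1, 1). The 30–60 min segment is 765 linear and 49 × 30 / ln 50 = 376 log; the flat last segment is 30 either way. AUE0-90min is 635 + 765 + 30 = 1430 linear and 1041 under the SAP rule, a difference of −27.2%.

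**Small fall, well above baseline** (0, 2, 10, 50, 80, 70). AUE0-90min is 4835 linear and 4832 under the SAP rule, a difference of −0.1%.

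**Early dip** (0, −3, 5, 50, 80, 70). If every falling segment is logged, the first segment needs the log of a non-positive ratio, so both AUE0-30min and AUE0-90min are undefined. If descending means after the peak, the dip is integrated linearly and AUE0-30min is −7.5 + 5 + 550 = 547.5.

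**The pre-dose rule does not help.** Setting the pre-dose value to zero on the adjusted curve only restates its starting point. Setting it to zero on raw glucose would cancel the baseline adjustment.

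**Consistency of the linear rule.** The linear area of the adjusted curve equals the raw linear area minus baseline × duration, whatever the sign. The log rule lacks this property. With an assumed baseline of 110 mg/dL and x = 1, linear integration gives 3200 on either scale. Linear-up/log-down gives 2717 on the adjusted curve but 3137 on raw glucose after subtracting 110 × 90.

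**The case against.** Three stronger readings are tempting, and the documents do not support them.

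- A reader might infer that the rule breaks because the curve starts at zero. It does not: a rise from zero uses the linear rule. Harm at the start needs both an early dip and the reading that every falling segment is logged. Table 3 speaks of one ascending and one descending part, and SAP 16.2 divides its rules at tmax, which fits the after-peak reading at least as well.
- A reader might infer that AUE is badly understated whenever glucose nears baseline. That confuses one segment with the endpoint. A 30-min segment from 60 loses about 20% at an end value of 10 and 53% at 1, but AUE0-90min as a whole loses 6% and 15%. The shortfall is also only relative to the linear rule; with samples 30 min apart, the true curve is unknown.
- A reader might infer that weak responders would lose their AUE. A small response that rises or stays above baseline is computable. The trigger is a fall to or below baseline.

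The best argument on the other side is that this may rarely happen. Every phase 2 patient rose by at least 20 mg/dL within 30 min (Protocol 5.1). Protocol 7.4.2 allows insulin for the induced hyperglycemia only from 90 min at Visits 2 and 4, so raised glucose is anticipated at the end of the window. The software may apply its own linear fallback. The analysis is descriptive, and SAP 16.3 and 16.4 tabulate PD by treatment and visit, not by ADA status.

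All of this limits the impact. It does not supply the missing rule: the SAP names no fallback, and the planned formula has no value for a profile that can occur.

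**Conclusion.** The point holds as a specification error in a descriptive secondary PD metric. As written, AUE0-90min cannot be calculated for a patient whose glucose is at or below its pre-dose value by 60 or 90 min. AUE0-30min is also exposed to an early dip if every falling segment is logged.

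Where the rule is defined but the curve ends near baseline, the size is the 3% to 27% reduction in AUE0-90min shown in the working. It is negligible when glucose stays well above baseline, and a late fall does not change AUE0-30min. These sizes rest on assumed profiles and are measured against the linear rule. The frequency cannot be derived from the documents.

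The primary ADA endpoint, CEmax and the 20 mg/dL increase endpoint do not use the trapezoid and are unaffected. The correction should be made because it is nearly free and protects the ADA-positive versus ADA-negative comparison in Protocol 7.6.1.

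**What to change.** In SAP 16.1, Table 3, specify the linear trapezoidal rule throughout for AUE0-30min and AUE0-90min, and state that the area is net, so that area below baseline counts as negative. Leave linear-up/log-down in Table 2 for drug concentrations.

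Net area is a choice that the SAP leaves open; it is the one that matches raw area minus baseline × duration. A narrower repair would be a linear fallback when either end value is zero or less, with the descending part defined. That removes the undefined case but keeps the reduction near baseline.

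The cost is one line in the SAP and a small programming change, with no new data. If the SAP is already final, document the change in the CSR, as SAP 1 provides for deviations from the plan.
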